12.2 Device Deficiency

The Device Deficiency (DD) definition is provided in Table 6: Adverse Event and Device Deficiency Definitions. DD information will be collected throughout the study and reported to Medtronic. Note that DD that result in an AE to the subject should be captured as an AE only.

DD that did not lead to an AE but could have led to a SADE (i.e., if suitable action had not been taken, if intervention had not been made, or if the circumstances had been less fortunate) require immediate reporting (see Table 10: Reporting Requirements).

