10.12 Recording Data

Data entered must be traceable to source documents. Source documentation is defined as the first time data appear, and may include original documents, data, and records (e.g., hospital records, clinical and office charts, procedure reports, laboratory notes, memoranda, subjects' diaries, recorded data from automated instruments, copies or transcriptions certified after verification as being accurate copies, ultrasound images, subject files, device data and records kept at other departments involved in the study).

In general, eCRFs (or paper copies) may not serve as source documents, unless specified below. Source documentation for data elements not routinely captured in medical records may vary from study site to study site; the study site may use source document worksheets.

The investigator must ensure the availability of source documents from which the information on the eCRFs was derived. The type and location of source documents should be documented. Where printouts of electronic medical records are provided as source documents, or where copies of source documents are retained as source documents, they should be certified. Certification must contain (1) the signature of the individual making the copy, (2) the date the copy was made and (3) a statement attesting to the accuracy and completeness of the copy.

The source documents must be made available for monitoring or auditing by Medtronic's representative or representatives of the competent authorities and other applicable regulatory agencies.

The CRF may be considered source for the following data collection elements:

- Enrollment Notification: Study site assigned subject identifier
- Baseline: Administrative information
- Device Accountability eCRF: All device accountability data points

- AE eCRF: Date study site became aware of event, Relatedness of adverse event, System modification information, Common Terminology Criteria for Adverse Events Classification
- DD eCRF: Date study site became aware of event
- Deviations: Reason for deviation

Electronic Data Capture (EDC)

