12.1 Adverse Events

All adverse events as well as all device deficiencies will be considered reportable for this study and will be collected after the subject is consented to participate in the study through study exit. The term “investigational device” is part of ISO 14155:2020 definitions. The term “investigational device” refers to any device used in the study including market released devices.

Adverse event terms are defined as follows:

- Device Related: An adverse event that results from the presence or performance (intended or otherwise) of any component of the TNM system
- Procedure Related: An adverse event that occurs due to any procedure related to the implantation or explant of the TNM system. The procedure is defined as the neurostimulator implant and/or explant procedures
- Study Aids Related: An adverse event that results from the presence or performance (intended or otherwise) of any study aids related to the TNM system
- Therapy Related: An adverse event related to therapy delivery by device e.g., device stimulation issue (normally therapy-related events resolve when the device is turned off or reprogrammed).

Adverse events that are classified as possible, probable, or causal are considered to be related for analysis purposes. Reporting of adverse events to Medtronic will occur on an AE eCRF. Each event must be reported separately. For AEs that require immediate reporting (see Table 10: Reporting Requirements), initial reporting may be done by phone or on the eCRF completing as much information as possible. The completed AE eCRF must be submitted to Medtronic as soon as possible.

Any medication/treatment associated with the treatment of an AE must be reported.

Subject deaths are also required to be reported in accordance with Table 10: Reporting Requirements.

All non-subject AEs (users or other persons as defined in Table 6) will be collected throughout the study duration.

Special considerations for adverse events and device deficiencies reporting:

- Normal expected complaints or symptoms reported during or following the procedure which are related to ordinary procedure or post-procedure care will be reported as adverse events; however, they will not be analyzed as device, procedure, therapy, or study aid-related adverse events unless there is a clinically significant change in severity or duration of symptoms, or the event requires clinical intervention that is different from ordinary procedure or post-procedure care.

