Device Deficiencies

Investigator shall submit to:

Medtronic	Submit or report as required per local reporting requirements.
FDA	Submit to FDA per local reporting requirement.
IRB	Submit to IRB per local reporting requirement.

Sponsor shall submit to:

FDA	Submit to FDA per local reporting requirement.
IRB	Submit to IRB per local reporting requirement.

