14.9 Safety Evaluation

All AEs and DDs will be collected throughout the study once the informed consent form is signed. AEs and DDs will be coded and summarized using the most recent version of Medical Dictionary for Regulatory Affairs (MedDRA). Severity will be assessed by the Investigator. Relatedness and seriousness of the events will be classified by the Investigator, CEC, and the Sponsor. Cases where the Investigator's classification does not match the CEC's classification will be displayed within the final report; however, the CEC's adjudication will be used for data analysis.

Adverse events and DDs that occur prior to implant will be summarized. Adverse events and DDs that occur on or after tibial neuromodulation implant date through study discontinuation will also be summarized; summaries specific to the timeframe from implant to the 6-month follow-up visit will be included. The denominator will be the number of subjects in the All Implanted analysis set. Adverse events in subjects with implant attempted but without full implant will also be summarized. Events that occur in subjects with an unsuccessful implant procedure will be included in the summaries. AEs and DDs will be summarized with number of events, number of subjects who experienced the event, and percentage of subjects who experienced one or more events.

15. Ethics

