## 7.10 Safety Evaluation

All AEs and DDs will be collected throughout the study once the informed consent form is signed. AEs and DDs will be coded using the most recent version of Medical Dictionary for Regulatory Affairs (MedDRA). Severity will be assessed by the Investigator. Relatedness and seriousness of the events will be classified by the Investigator, CEC, and the Sponsor. Cases where the Investigator's classification does not match the CEC's classification will be displayed within the final report; however, the CEC's adjudication will be used for data analysis.

Adverse events that occur prior to implant will be summarized. Adverse events that occur on or after tibial neuromodulation implant date through study discontinuation will also be summarized; summaries specific to the timeframe from implant to the 6-month follow-up visit will be included as well as those that include all post-implant follow-up (i.e. though "24 months"). AE tables summarizing adverse device effects (ADE) will also be included. ADE are events deemed related to the neurostimulator, procedure, external device, study aids, or therapy. In addition to tables of overall ADE, summaries by the individual relatedness component will be summarized using the following categories: procedure-related, device-related (neurostimulator/external device), therapy-related, and study aids-related. Resolution (number of events/percentage) of ADE will be summarized using similar time groupings to other summaries. ADE will also be summarized grouping the events by Common Terminology Criteria for Adverse Events (CTCAE) grade.

The denominator for post-implant summaries will be the number of subjects in the All Implanted analysis set, while for pre-implant summaries it will include all enrolled subjects. Events occurring on date of implant will be considered post-implant events.

Summaries of serious adverse events (SAEs) will also be completed in similar ways to AE summaries. Unanticipated Serious Adverse Device Effects (USADE) will be described. Adverse events in subjects with implant attempted but without full implant will also be summarized as part of additional AE summary tables of the Full Analysis Set. Device-related deaths and system modifications will be summarized in detail.

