Device deficiencies will be summarized by device type (i.e., communicator, handset, neurostimulator, wireless recharger/charging dock, external patient accessories, and sterile procedure accessories) through the 24 month visit.

Events will be summarized with number of events, number of subjects who experienced the event, and percentage of subjects who experienced one or more events.

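### Device deficiencies that cause a subject adverse event are left out of the planned deficiency tables, and the immediate-reporting rule for potentially serious deficiencies cites a table that does not contain it

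*Protocol*

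**What the plan says.** Protocol 12.1 sets the general rule: "All adverse events as well as all device deficiencies will be considered reportable for this study". Table 6 defines a deficiency by the inadequacy of the device, including malfunctions and use errors, whether or not anyone was harmed. Section 12.2 then adds a capture rule: "Note that DD that result in an AE to the subject should be captured as an AE only".

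On analysis, protocol 14.9 states: "AEs and DDs will be summarized with number of events, number of subjects who experienced the event", together with a percentage of subjects. SAP 7.10 is more specific: "Device deficiencies will be summarized by device type". It lists six types, among them the neurostimulator, the handset, the communicator and the recharger with its dock, through 24 months. ADEs are broken down as "procedure-related, device-related (neurostimulator/external device), therapy-related, and study aids-related".

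On timing, section 12.2 says that deficiencies which did not lead to an AE but could have led to a SADE "require immediate reporting (see Table 10: Reporting Requirements"). In the Device Deficiencies block of Table 10 (section 12.5.2), the entry for investigator to sponsor reads: "Submit or report as required per local reporting requirements".

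**The concern.** A reader of a table of deficiencies by device type will take it as the count of component failures in the study. Under the capture rule it leaves out the failures that produced a subject AE, which are the ones of most interest. Those cases move to the AE tables, where nothing planned separates an AE caused by a malfunction from, say, pain over an implant that works normally. For a significant-risk implant in a pre-market study, two basic safety questions are how often each component fails and how often a failure harms a subject. The planned tables do not fully answer the first and do not answer the second.

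The timing problem is smaller and separate. A site that follows the cross-reference from 12.2 to Table 10 does not find the rule it was sent to find.

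**Working it through.** The plan states no figure on this point, so there is nothing to reproduce. The check sets the provisions side by side.

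**Part 1: the deficiency count**

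1. Capture. Protocol 12.2 sends a deficiency with a resulting subject AE to the AE record only. Deficiencies have their own form: protocol 10.12 lists, among items for which the CRF may be the source, "DD eCRF: Date study site became aware of event".
2. Analysis of deficiencies. Neither protocol 14.9 nor SAP 7.10 has a step that brings AE-only deficiencies into the DD summary, and neither has a statement that they are left out.
3. Consequence. For any device type, write
   - N(all) = deficiencies that occurred and were noticed,
   - N(AE) = those that resulted in a reportable AE to the subject,
   - N(table) = those held as DD records.

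   If the rule is followed, N(table) = N(all) − N(AE), so the event count is low by exactly N(AE). The count of affected subjects is low by those whose only deficiency of that type was captured as an AE. No document gives N(all) or N(AE), so the size cannot be stated.
4. Can the AE tables recover it? Table 6 makes an AE due to a malfunction an ADE, so the event is counted. But Table 9 classifies relatedness only as device, therapy, procedure or study aid, and SAP 7.10 reports neurostimulator and external device as one category. The ADE breakdown has no row for AEs arising from a deficiency, and it does not separate handset, communicator and recharger. The link from deficiency to harm is therefore not shown in either set of tables.

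**Part 2: the reporting time**

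| Place | What it provides for a deficiency with SADE potential |
|---|---|
| Protocol 12.2 | Immediate reporting, with a reference to Table 10 |
| Table 9 (12.5.1) | A formal class, assigned by both investigator and sponsor |
| Table 10, Device Deficiencies block | No such category; local requirements only, for sponsor, FDA and IRB |
| Table 10, SADE block | Immediate, with a limit of 10 calendar days, but for SADEs that have occurred |
| 12.5.1, emergency contact sentence | Names UADE, USADE, SAE and SADE; not this class |
| Protocol 12.7 | Product complaints to be reported immediately, by a separate route and with no number of days |

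The Device Deficiencies block of Table 10 reads as complete, so the missing entry does not look like a loss in text extraction. Section 12.2 and the table it cites disagree.

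**The case against.** The strongest reply is that recording each occurrence once is an ordinary convention that avoids double counting, and that no harm goes unreported. Resulting AEs are tabulated by relatedness, resolution and CTCAE grade. System modifications are summarised in detail. A sponsor representative reviews every AE and DD, and the Clinical Events Committee reviews related and serious AEs and AE trends. No endpoint or pausing rule uses DD counts: the pausing rules count explants after migration or erosion. Calling all deficiencies reportable does not mean that each needs its own DD form, so 12.1 and 12.2 do not strictly contradict each other. All of this stands. It does not make the DD table complete, and two linked records shown in separate tables would double count nothing within either.

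The eCRFs are not among the documents, and the list in protocol 10.12 covers only items for which the CRF may be the source. A device or deficiency field may therefore exist on the AE form. SAP 7.10 names neurostimulator and external device separately when it defines ADEs, which suggests that the two may be assessed separately. The point is that no document describes such a field or plans a table from it.

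Three stronger readings are tempting, and the documents do not support them.

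- A reader might infer that every deficiency in the DD table is harmless. Protocol 12.1 excludes worsening of OAB symptoms, and stimulation effects that are not clinically significant, from reportable AEs. A failure with only those effects stays a DD. So does one that affects a user or another person, because the rule in 12.2 concerns AEs to the subject.
- A reader might infer that deficiencies with SADE potential have no reporting time at all. Section 12.2 itself says immediate, and 12.7 gives a parallel immediate route for product complaints. The defect is that the table cited does not carry the rule.
- A reader might try to put a percentage on the undercount. Any such figure would only restate an assumed share of harmful deficiencies.

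**Conclusion.** The concern holds in a limited form. If section 12.2 is followed, the DD summaries in protocol 14.9 and SAP 7.10 understate deficiencies, by device type, by the number that caused a reportable subject AE. The direction is certain whenever such a case occurs; the size is unknown. Two assumptions underlie this: that AE-only capture means no DD record exists, and that no unseen field or programming step restores these cases. Both are the natural reading of the text, but the omission from the table is inferred rather than stated. What is lost is the full component count and the link from deficiency to harm; the harm itself is not lost, and the primary efficacy result is untouched.

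The mismatch between section 12.2 and Table 10 needs no assumption. It can be read directly from the text and should be reconciled. Both matters should be corrected, though neither threatens the trial's main conclusion.

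**What to change.** 1. In protocol 12.2 and on the AE form, flag any AE caused by a deficiency and record the device type. Completing both forms with a link between them would serve equally well.
2. In SAP 7.10, tabulate all deficiencies by device type in two columns: those that led to a subject AE and those that did not. Leave the AE and ADE counts as they are. If the AE-only rule is kept without a flag, the least that is needed is a footnote saying that the DD table excludes deficiencies captured as AEs. That would make the table honest but not complete.
3. In Table 10, add a row for deficiencies with SADE potential that carries the timing section 12.2 already states, so that text, Table 9 and Table 10 agree.

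The cost is one extra field, or a second form for what are likely to be few events, plus one table column and one table row. DD counts will be slightly higher than under the present rule, which is the intended effect.

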12.3 Processing Updates and Resolution

For any changes in status of a previously reported adverse event or DD (i.e., change in actions taken, change in outcome, change in relatedness), information needs to be updated on, or added to the original AE or DD eCRF. All AEs must be followed until the AE has been resolved, is unresolved with no further actions planned, the subject dies or exits the study, or until study closure, whichever occurs first.

In the event that a subject is exited from the study prior to their completion in the study, it is recommended to continue following the subject until all unresolved related AEs, are resolved or unresolved with no further actions planned

At the time of study exit, all collected adverse events that are unresolved must be reviewed and an update to the original AE must be reported.

12.4 Definitions/Classifications

Where the definition indicates “device”, it refers to any investigational device or system component used in the study. Table 6: Adverse Event and Device Deficiency Definitions contains adverse event and device deficiency definitions.

Table 6: Adverse Event and Device Deficiency Definitions

General	
Adverse Event (AE) (ISO 14155:2020, 3.2)	
Untoward medical occurrence, unintended disease or injury, or untoward clinical signs (including abnormal laboratory findings) in subjects, users, or other persons, whether or not related to the investigational medical device and whether anticipated or unanticipated
 
NOTE 1: This definition includes events related to the investigational medical device or the comparator.
 
NOTE 2: This definition includes events related to the procedures involved.
 
NOTE 3: For users or other persons, this definition is restricted to events related to the use of investigational medical devices or comparators

Adverse Device Effect (ADE) (ISO 14155:2020, 3.1)	
AE related to the use of an investigational medical device
 
NOTE 1: This definition includes AEs resulting from insufficient or inadequate instructions for use, deployment, implantation, installation, or operation, or any malfunction of the investigational medical device.
 
NOTE 2: This definition includes any event resulting from use error or from intentional misuse of the investigational medical device.
 
NOTE 3: This includes 'comparator' if the comparator is a medical device.
 
STUDY SPECIFIC NOTE: These are considered device related, therapy related, study aid related and/or procedure related.

Device Deficiency (DD) (ISO 14155:2020, 3.19)	
Inadequacy of a medical device with respect to its identity, quality, durability, reliability, usability, safety, or performance.
 
NOTE 1: DD include malfunctions, use errors and inadequacy in the information supplied by the manufacturer including labeling.
 
NOTE 2: This definition includes device deficiencies related to the investigational medical device or the comparator.

Seriousness	
Serious Adverse Event (SAE) (ISO 14155:2020, 3.45)	
AE that led to any of the following
 
a) death,
 
b) serious deterioration in the health of the subject, users or other persons as defined by one or more of the following:
 
1) a life-threatening illness or injury, or2) a permanent impairment of a body structure or a body function, including chronic disease, or3) in-patient or prolonged hospitalization, or4) medical or surgical intervention to prevent life-threatening illness or injury or permanent impairment to a body structure or a body function, 
c) fetal distress, fetal death or a congenital abnormality or birth defect including physical or mental impairment
 
NOTE 1: Planned hospitalization for a pre-existing condition, or a procedure required by the CIP, without serious deterioration in health, is not considered an SAE.
 
STUDY SPECIFIC NOTE: For this study, all adverse events will be collected; however, adverse events related to infections and neurostimulator explants will be considered non-serious unless the investigator deems that clinical sequela is present which meets the seriousness definition outlined in the CIP.

Serious Adverse Device Effect (SADE) (ISO 14155:2020, 3.44)	Adverse device effect that has resulted in any of the consequences characteristic of a serious adverse event.
Unanticipated Adverse Device Effect (UADE) (21 CFR 812.3(s))	Any serious adverse effect on health or safety or any life-threatening problem or death caused by, or associated with, a device, if that effect, problem, or death, was not previously identified in a nature, severity, or degree of incidence in the investigational plan or application (including a supplementary plan or application), or any other unanticipated serious problem associated with a device that relates to the rights, safety, or welfare of subjects.

Unanticipated Serious Adverse Device Effect (USADE) (ISO 14155:2020, 3.51)	
Serious adverse device effect which by its nature, incidence, severity, or outcome has not been identified in the current risk assessment
 
NOTE 1: Anticipated serious adverse device effect (ASADE) is an effect which by its nature, incidence, severity, or outcome has been identified in the risk assessment.

Serious Health Threat (ISO 14155:2020, 3.46)	
Signal from any adverse event or device deficiency that indicates an imminent risk of death or a serious deterioration in the health in subjects, users, or other persons, and that requires prompt remedial action for other subjects, users, or other persons
 
NOTE 1: This would include events that are of significant and unexpected nature such that they become alarming as a potential serious health hazard or possibility of multiple deaths occurring at short intervals.

Table 7: Adverse Event Relatedness

Relatedness	
Term	Definition
Not Related	
Relationship to the device or procedures can be excluded when:
 
 - the event is not a known¹ side effect of the product category the device belongs to or of similar devices and procedures; - the event has no temporal relationship with the use of the investigational device or the procedures; - the serious event does not follow a known response pattern to the medical device (if the response pattern is previously known) and is biologically implausible; - the discontinuation of medical device application or the reduction of the level of activation/exposure - when clinically feasible – and reintroduction of its use (or increase of the level of activation/exposure), do not impact on the serious event; - the event involves a body-site or an organ not expected to be affected by the device or procedure; - the serious event can be attributed to another cause (e.g., an underlying or concurrent illness/ clinical condition, an effect of another device, drug, treatment or other risk factors); - the event does not depend on a false result given by the investigational device used for diagnosis², when applicable; - harms to the subject are not clearly due to use error; - In order to establish the non-relatedness, not all the criteria listed above might be met at the same time, depending on the type of device/procedures and the serious event. 
1 When the event is not a known side effect of the product category the device belongs to or of similar devices and procedures, generally is considered “not related”. Yet, the unexpected effect shall not be excluded from evaluation and reporting.
 
2 If an investigational device gives an incorrect diagnosis, the patient might, for example, receive an unnecessary treatment and incur all the risks that accompany that treatment, or might be incorrectly diagnosed with a serious disease. In other cases, the patient might not receive an effective treatment (thereby missing out on the benefits that treatment would confer) or might not be diagnosed with the correct disease or condition.

Relatedness	
Term	Definition
Possible	The relationship with the use of the investigational device is weak but cannot be ruled out completely. Alternative causes are also possible (e.g., an underlying or concurrent illness/ clinical condition or/and an effect of another device, drug, or treatment). Cases where relatedness cannot be assessed, or no information has been obtained should also be classified as possible.
Probable	The relationship with the use of the investigational device seems relevant and/or the event cannot reasonably be explained by another cause, but additional information may be obtained.
Causal Relationship	
The serious event is associated with the investigational device or with procedures beyond reasonable doubt when:
 
 - the event is a known side effect of the product category the device belongs to or of similar devices and procedures; - the event has a temporal relationship with investigational device use/application or procedures; - the event involves a body-site or organ that 
 o the investigational device or procedures are applied to; o the investigational device or procedures have an effect on; - the serious event follows a known response pattern to the medical device (if the response pattern is previously known); - the discontinuation of medical device application (or reduction of the level of activation/exposure) and reintroduction of its use (or increase of the level of activation/exposure), impact on the serious event (when clinically feasible); - other possible causes (e.g., an underlying or concurrent illness/ clinical condition or/and an effect of another device, drug or treatment) have been adequately ruled out; - harm to the subject is due to error in use; - the event depends on a false result given by the investigational device used for diagnosis¹, when applicable; - In order to establish the relatedness, not all the criteria listed above might be met at the same time, depending on the type of device/procedures and the serious event. 
1 If an investigational device gives an incorrect diagnosis, the patient might, for example, receive an unnecessary treatment and incur all the risks that accompany that treatment, or might be incorrectly diagnosed with a serious disease. In other cases, the patient might not receive an effective treatment (thereby missing out on the benefits that treatment would confer might not be diagnosed with the correct disease or condition.

Table 8: Common Terminology Criteria for Adverse Events (CTCAE)²⁴

Grades	Definition
Grade 1	Mild; asymptomatic or mild symptoms; clinical or diagnostic observations only; intervention not indicated
Grade 2	Moderate; minimal, local or noninvasive intervention indicated; limiting age-appropriate instrumental ADL*
Grade 3	Severe or medically significant but not immediately life-threatening; hospitalization or prolongation of hospitalization indicated; disabling; limiting self-care ADL**
Grade 4	Life-threatening consequences; urgent intervention indicated.
Grade 5	Death related to an AE

*Activities of Daily Living (ADL)

*Instrumental ADL refer to preparing meals, shopping for groceries or clothes, using the telephone, managing money, etc.

**Self-care ADL refer to bathing, dressing and undressing, feeding self, using the toilet, taking medications, and not bedridden.

